1. ABSTRACT

Background: Exercise snacks have emerged as a promising strategy to improve physical function in older adults. However, the optimal fragmentation pattern (i.e., how to distribute a fixed daily volume of exercise across the day) remains unknown. Furthermore, the effects of resistance-based exercise snacks on cognitive function in pre-frail older adults have not been investigated.

Objective: To compare the effects of four different fragmentation patterns of a three-exercise resistance snack (sit-to-stand, squat, and heel raise) on lower limb strength, dynamic balance, and executive cognitive function in community-dwelling pre-frail older adults.

Design: Four-arm parallel-group randomized controlled pilot trial.

Participants: 60 community-dwelling pre-frail older adults (Fried Frailty Phenotype score 1-2, aged ≥ 65 years).

Interventions: All groups perform a fixed total daily volume of 15 repetitions per exercise (sit-to-stand, squat, and heel raise), resulting in 45 total repetitions per day. The only difference between groups is the fragmentation pattern:

- G1 (highly fragmented): 1 repetition of each exercise per bout, 15 bouts/day (~30 seconds per bout)
- G2 (moderately fragmented): 3 repetitions of each exercise per bout, 5 bouts/day (~90 seconds per bout)
- G3 (lowly fragmented): 5 repetitions of each exercise per bout, 3 bouts/day

(~2.5 minutes per bout)

- G4 (consecutive control): 15 repetitions of each exercise per bout, 1 bout/day (~7.5 minutes per bout)

The intervention period is 8 weeks.

Outcome Measures: Primary outcomes include lower limb strength (30-second chair stand test) and dynamic balance (Timed Up and Go test). Secondary outcomes include comprehensive physical function (Short Physical Performance Battery), executive function (Stroop Color-Word Test and Trail Making Test), and falls efficacy (modified Falls Efficacy Scale). Feasibility outcomes include adherence, acceptability, and adverse events.

Data Analysis: A 4×3 mixed ANOVA will be used to compare group differences. Effect sizes (Cohen's d , η^2) will be estimated to inform a future definitive randomized controlled trial.

Expected Results: This pilot trial will provide preliminary evidence on the dose-response relationship between exercise snack fragmentation patterns and both physical and cognitive outcomes in pre-frail older adults.

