3. STUDY DESIGN

Design Overview

- **Design:** Four-arm parallel-group randomized controlled pilot trial

- **Allocation Ratio:** 1:1:1:1
- **Masking:** Assessor-blind (outcome assessors unaware of group assignment)
- **Intervention Period:** 8 weeks
- **Assessment Time Points:** Baseline (Week 0), Mid-intervention (Week 4), Post-intervention (Week 8)

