4.3 Sample Size

As a pilot trial, formal power calculation is not performed. Fifteen participants per group (total N=60) will be recruited. Anticipating a 20-25% attrition rate, approximately 45 participants (11-12 per group) are expected to complete the 8-week intervention.

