10.2 Statistical Methods

Analysis Purpose	Statistical Method
Baseline characteristics comparison	One-way ANOVA or chi-square test
Within-group changes	Paired t-test or Wilcoxon signed-rank test
Between-group differences	4 × 3 mixed ANOVA, post-hoc Tukey HSD
Trend analysis	Polynomial contrast (linear, quadratic)
Effect sizes	Cohen's d (within-group), η^2 (between-group)

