10.4 Sample Size Justification

As a pilot trial, formal power calculation is not performed. Fifteen participants per group (total N=60) will allow estimation of effect sizes (width of 95% CI for Cohen's d) and feasibility outcomes (recruitment, retention, adherence).

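### The named effect sizes, within-group Cohen's d and uncorrected eta-squared, do not give the between-arm difference a definitive trial would need

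*Protocol*

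**What the plan says.** The design is a "Four-arm parallel-group randomized controlled pilot trial". All arms exercise, with the same daily repetitions, and differ only in how these are split into bouts (Protocol 5.1).

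- The abstract says that effect sizes, given there as Cohen's d and eta-squared, "will be estimated to inform a future definitive randomized controlled trial".
- Section 10.2 assigns them: "Cohen's d (within-group), η^2 (between-group"). Eta-squared is therefore the only between-group effect size named.
- The same table gives "4 × 3 mixed ANOVA, post-hoc Tukey HSD" for between-group differences, polynomial contrasts for trend, and "Paired t-test or Wilcoxon signed-rank test" for within-group change.
- Section 10.4 gives no power calculation. It says that 15 per arm "will allow estimation of effect sizes (width of 95% CI for Cohen's d") and of feasibility outcomes. It states no width and does not say there which d is meant.
- Section 4.3 adds: "Anticipating a 20-25% attrition rate, approximately 45 participants (11-12 per group) are expected to complete the 8-week intervention".

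**The concern.** The study objectives (section 2.4) are about comparing patterns, so a later trial needs a between-arm difference, its uncertainty, and the SD and correlation that set the sample size. Neither named effect size supplies these.

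Within-group d is the change from baseline divided by an SD. With no untreated arm, it contains the shared exercise effect, practice on the tests and regression to the mean. Four large values say nothing about whether the patterns differ.

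Eta-squared does concern the arms, but it cannot be negative, and in a small four-arm sample it lies above zero by chance alone. Someone who takes it as an estimate of the true effect would plan a trial on noise.

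The precision argument in 10.4 has the same gap. Read with 10.2, the d whose interval supports N = 60 is the within-group one, which does not describe how precisely two arms can be compared.

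**Working it through.** **Inputs from the protocol:** 4 arms, 15 per arm, N = 60 (10.4); 3 visits (section 3); 20-25% attrition (4.3); all randomized participants in the primary analysis, with multiple imputation (10.1, 10.3). **Assumed:** alpha 0.05, power 80%, correlation between visits 0.5 to 0.8, and in the illustration a gain of 0.5 baseline SD in every arm.

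**1. The protocol's own figure.** 60 × 0.75 = 45 and 60 × 0.80 = 48 completers; per arm 15 × 0.75 = 11.25 and 15 × 0.80 = 12. The stated 45 (11-12 per group) is reproduced, at the 25% end.

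**2. Eta-squared when the arms do not differ.** SSB/(SSB + SSW) follows a Beta(df1/2, df2/2) distribution, with mean df1/(df1 + df2).

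- Group effect, or one-way analysis of change: df 3 and N − 4, mean 3/(N − 1).
- Group × time, partial: df 6 and 2(N − 4), mean 6/(6 + 2(N − 4)) = 3/(N − 1) again.

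| N | Null mean | f = sqrt(mean/(1 − mean)) | Implied four-arm trial, 80% power |
|---|---|---|---|
| 60 | 3/59 = 0.051 | 0.231 | 52 per arm, 208 |
| 48 | 3/47 = 0.064 | 0.261 | 41 per arm, 164 |
| 45 | 3/44 = 0.068 | 0.271 | 39 per arm, 156 |

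The last column uses the noncentral F test with noncentrality f² × N. At N = 60 the 95th percentile of null eta-squared is 0.129 for group and 0.105 for partial group × time. The rows for 48 and 45 describe completers; the planned primary analysis keeps all 60.

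**3. Which eta-squared.** In a simulation of 20,000 null trials (4 arms × 15 × 3 visits, same gain in every arm), the means were:

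| Form | Correlation 0.5 | Correlation 0.8 |
|---|---|---|
| Partial, group | 0.051 | 0.051 |
| Partial, group × time | 0.051 | 0.051 |
| One-way on change | 0.051 | 0.051 |
| Classical (total SS), group | 0.032 | 0.042 |
| Classical (total SS), group × time | 0.016 | 0.007 |
| Omega-squared or epsilon-squared, on change | about 0.000 | about 0.000 |

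**4. Within-group d in the same null trials.** Every arm gains 0.5 baseline SD and the between-arm effect is zero. Within-group d averages 0.53 on the baseline SD. On the change SD it averages 0.53 (correlation 0.5) to 0.84 (correlation 0.8).

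**5. Precision.** The approximate 95% interval width for a between-arm d, at d = 0, is 2 × 1.96 × sqrt(2/n):

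- n = 15: 3.92 × sqrt(2/15) = 1.43
- n = 12: 3.92 × sqrt(2/12) = 1.60
- n = 11: 3.92 × sqrt(2/11) = 1.67

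For a within-group d on the change SD, the width at d = 0 is 3.92 × sqrt(1/15) = 1.01 at n = 15. The between-arm interval is then sqrt(2) = 1.41 times as wide. The within-group figure depends on the standardizer, which the protocol does not name.

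**The case against.** The best defence is that between-arm estimation is already planned. The mixed ANOVA with Tukey HSD can yield pairwise mean differences with simultaneous intervals, and the polynomial contrasts address trend. This stands in part: a reader might infer that the plan yields no between-arm estimate, and the document does not support that. But Tukey HSD is listed as a post-hoc test, and the effect-size row, which carries the stated planning purpose, names only the two measures above.

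Four other stronger readings also go too far:

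- **That eta-squared averages 0.05 under the null without qualification.** This holds for the partial or one-way form only. Section 10.2 writes plain eta-squared, and the classical group × time form averages 0.007 to 0.016.
- **That the definitive trial will be sized from these numbers, or that they are the pilot's main product.** The abstract says only that they will inform it, and section 6.3 sets five feasibility outcomes with success criteria.
- **That arms will be compared through their separate paired tests.** Section 10.2 gives between-group inference its own row, and nothing says paired p-values will be set against each other.
- **That 10.4 states too favourable a precision.** It states no width, and reading its d as within-group is an inference from the label in 10.2.

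It is also fair that the standardizer, the bias-corrected measure and the covariate adjustment could be left to a statistical analysis plan, and that a pilot needs no power calculation. Neither answers the point that the protocol itself labels d as within-group and gives effect-size estimation as a reason for N.

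**Conclusion.** The concern holds in a limited form. The protocol fixes a within-group d, which cannot estimate a difference between patterns, and an eta-squared of unstated form that is biased upward. With no arm difference at N = 60 the mean is 0.051 for the partial or one-way form, or about 0.03-0.04 (group) and 0.007-0.016 (group × time) for the classical form under assumed correlations of 0.5 to 0.8. The implied 208 participants rests on the 0.051 form and on the assumed alpha and power. It shows what a face-value reading would lead to, not what the protocol says it will do.

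This is a should-fix. The planned data and model can already supply the right quantities; what is wrong is which effect sizes are named and which d supports N.

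**What to change.** In 10.2, make the reported effect size the baseline-adjusted between-arm mean difference at Week 8 with a 95% interval, for example each of G1, G2 and G3 versus G4. The planned all-pairwise and trend analyses can stay. Report with it the outcome SD and the baseline-to-follow-up correlation. If a measure of variance explained is kept, use omega-squared or epsilon-squared with an interval, and say which term of the model it refers to. Keep within-group d as descriptive only.

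In 10.4, say that the d is between-arm and give its approximate 95% interval width at d = 0: 1.43 at 15 per arm and about 1.6 to 1.7 at 11 to 12 completers per arm.

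The cost is wording in two sections and slightly more reporting; no extra participants, visits or data are needed. The protocol would then show a visibly wide interval, which is an honest picture of what 15 per arm can say about differences between patterns.

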10.3 Missing Data Handling

- Multiple imputation (5 imputations) for random missing data
- Sensitivity analysis comparing ITT and PP results

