10. STATISTICAL ANALYSIS

10.1 Analysis Populations

Population	Definition	Purpose
ITT (Intention-to-Treat)	All randomized participants, analyzed according to original group assignment	Primary analysis
PP (Per-Protocol)	Participants with adherence $\geq 80\%$	Sensitivity analysis
Safety Population	Participants who received at least one intervention session	Adverse event analysis

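### Five imputations, with 20-25% attrition expected, is valid but leaves avoidable Monte Carlo noise; raising the number is a minor improvement at almost no cost

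*Protocol*

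**What the plan says.** Protocol section 10.3 (Missing Data Handling) fixes the number of imputations: "Multiple imputation (5 imputations) for random missing data". It gives no reason for that number.

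Three other sections determine how much rests on it:
- Section 4.3 (Sample Size): "Fifteen participants per group (total N=60) will be recruited", and then "Anticipating a 20-25% attrition rate, approximately 45 participants (11-12 per group) are expected to complete the 8-week intervention".
- Section 10.1 (Analysis Populations): the primary analysis is intention-to-treat, defined as "All randomized participants, analyzed according to original group assignment". Participants without a Week 8 value therefore enter the primary analysis through imputation.
- Section 10.2 (Statistical Methods): groups are compared by "4 × 3 mixed ANOVA, post-hoc Tukey HSD".

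The trial has no power calculation ("As a pilot trial, formal power calculation is not performed", section 4.3). Section 10.4 justifies the sample size instead by what 60 participants make estimable: the number "will allow estimation of effect sizes (width of 95% CI for Cohen's d) and feasibility outcomes".

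**The concern.** Five imputations loses little efficiency in the point estimate. The standard error, degrees of freedom, interval and p-value are less stable, because the between-imputation variance is then estimated on only 4 degrees of freedom. Two things follow. The interval is somewhat wider than the data require, and re-running the same imputation with another seed gives a different interval and p-value.

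This matters here because section 10.4 names the width of a 95% interval as a product of the trial, and section 10.2 plans significance tests. With up to about a quarter of participants lost, a comparison close to a conventional threshold could fall on either side of it by the choice of seed alone.

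**Working it through.** **1. The plan's own figure.** Completers = N × (1 − attrition). At 25%: 60 × 0.75 = 45, or 11.25 per group. At 20%: 60 × 0.80 = 48, or 12 per group. The stated figure of about 45 (11-12 per group) is reproduced; 45 itself corresponds to the 25% end.

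**2. Inputs.**
- M = 5 (section 10.3); 60 participants in 4 groups (section 4.3). Complete-data degrees of freedom for one contrast: 60 − 4 = 56.
- Fraction of missing information (FMI): not in the protocol, so assumed. Attrition of 20-25% suggests 0.20-0.25 if earlier visits help little. Simulated three-visit data with that dropout gave mean FMI of 0.16-0.22, because earlier visits carry information. The working range is 0.16-0.25, with 0.10 and 0.40 as outer values.
- Two-sided 0.05 as the reference threshold: assumed. The protocol states a 95% interval but no alpha.

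**3. Interval width.** Scale the total variance at unlimited M to 1, so the within-imputation variance is U = 1 − FMI and the between-imputation variance is B = FMI. Rubin's rules give T = U + (1 + 1/M)B. With λ = (1 + 1/M)B/T, the Barnard-Rubin degrees of freedom are ν = 1/[λ²/(M − 1) + 1/((57/59) × 56 × (1 − λ))]. The half-width is t(0.975, ν) × √T.

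Worked case, FMI 0.25 and M = 5:
- T = 0.75 + 1.2 × 0.25 = 1.05, and λ = 0.30/1.05 = 0.286.
- The two components of ν are 4/0.286² = 49.0 and 54.10 × 0.714 = 38.6, so ν = 21.6.
- Half-width = 2.076 × √1.05 = 2.127. At unlimited M, ν = 40.6 and the half-width is 2.020. The ratio is 1.053.

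Excess width over unlimited M:

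| FMI | M = 5 | M = 25 | M = 50 |
|---|---|---|---|
| 0.10 | 1.5% | 0.3% | 0.1% |
| 0.16 | 2.8% | 0.5% | 0.2% |
| 0.20 | 3.8% | 0.6% | 0.3% |
| 0.25 | 5.3% | 0.9% | 0.4% |
| 0.40 | 11.1% | 1.8% | 0.9% |

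As a cross-check, simulated data with 4 × 15 participants, three visits and 20-25% dropout gave intervals 3.2-4.7% wider at M = 5.

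**4. Seed-to-seed variation.** The Monte Carlo error of the pooled estimate, in units of its standard error, is √(FMI/M). At M = 5 this is √(0.16/5) = 0.18 to √(0.25/5) = 0.22. At M = 50 it is 0.06 to 0.07.

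To see the effect on intervals and p-values, the M imputed estimates were drawn repeatedly for one fixed data set whose p-value at unlimited M is 0.03, and pooled as in step 3:

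| FMI | M | Coefficient of variation of half-width | p: central 95% of seeds | Seeds with p ≥ 0.05 |
|---|---|---|---|---|
| 0.16 | 5 | 8% | 0.011-0.092 | 23% |
| 0.20 | 5 | 10% | 0.010-0.109 | 28% |
| 0.25 | 5 | 13% | 0.008-0.130 | 33% |
| 0.16 | 50 | 2% | 0.022-0.041 | about 0% |
| 0.20 | 50 | 2% | 0.021-0.043 | about 0% |
| 0.25 | 50 | 3% | 0.020-0.046 | about 1% |

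With M = 25 at FMI 0.25 the p-value range is 0.017-0.056.

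**The case against.** The strongest case against is that nothing here is invalid. Rubin's rules already carry the (1 + 1/M) term and reduced degrees of freedom, so five imputations gives an unbiased estimate and coverage close to nominal. That stands. The excess width is the price of correct allowance for few imputations, and it is small.

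A reader might infer that the trial's conclusions could turn on the seed. The protocol does not support this. It states no alpha and no efficacy decision rule, and its only success criteria (section 6.3) are recruitment, retention, adherence, acceptability and safety. None of these uses imputed efficacy data. The p-value ranges above describe a result chosen to be near 0.05; a result far from it would stay on the same side for almost any seed.

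A reader might also fault the plan for omitting a seed, an imputation model and pooling rules. Those details commonly belong in a statistical analysis plan, which may exist and is not shown. Only the stated number is open to criticism.

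Finally, the calculation pools a single contrast. The plan specifies a mixed ANOVA with Tukey comparisons and, in section 10.2, Cohen's d within groups. The percentages are therefore a guide to size, not exact values for those analyses. The choice of 50 rather than 25 is partly preference, and no finite number removes dependence on the seed altogether.

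**Conclusion.** The point holds as a minor improvement at almost no cost. Fixing five imputations is defensible in validity but needlessly noisy for the attrition the protocol expects. The width penalty is modest; the dependence of borderline p-values on the seed is the more substantial part.

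The figures rest on the assumed FMI range, on missing Week 8 values occurring at about the stated attrition rate, and on a single contrast with 56 complete-data degrees of freedom. If participants who stop exercising still attend assessments, or if earlier visits predict Week 8 strongly, the effect shrinks towards the FMI 0.10 row. If FMI is higher, it grows.

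**What to change.** In section 10.3, replace the number 5 with at least 50 imputations, run with a seed fixed in advance. Twenty-five would already bring the excess width below 1% across the assumed FMI range of 0.16-0.25; 50 also keeps the p-value of a borderline result within a narrow band. Fixing the seed alone is not enough: it makes the result repeatable but leaves it an arbitrary draw from the wide range shown for M = 5.

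The cost is one number in the text and code, and minutes of computing for 60 participants. Recruitment, assessments and design do not change.

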10.4 Sample Size Justification

As a pilot trial, formal power calculation is not performed. Fifteen participants per group (total N=60) will allow estimation of effect sizes (width of 95% CI for Cohen's d) and feasibility outcomes (recruitment, retention, adherence).

11. SAFETY

11.1 Adverse Event Monitoring

Event Type	Definition	Management
Fall	Unexpected contact with ground	Assess cause, modify protocol
Muscle strain	Persistent pain >24 hours post-exercise	Rest, heat therapy
Joint pain	Sharp pain in knee/hip joint	Stop exercise, assess movement
Dizziness	Lightheadedness post-exercise	Rest, monitor blood pressure

11.2 Early Termination Criteria

- One or more serious adverse events occur
- Attrition rate >40% in any group
- Participant voluntarily withdraws

12. ETHICAL CONSIDERATIONS

12.1 Ethical Approval

- The protocol has been reviewed and approved by the Institutional Review Board of [Institution Name]
- Approval number: [To be filled]
- Approval date: [To be filled]

12.2 Informed Consent

- All participants will provide written informed consent
- The informed consent form includes: study purpose, procedures, risks, benefits, confidentiality, and voluntary withdrawal

12.3 Data Confidentiality

- Participant data will be anonymized
- Only the research team will have access to raw data

12.4 Clinical Trial Registration

- This study is registered at [ClinicalTrials.gov](https://clinicaltrials.gov)
- NCT number: [To be assigned]

